9.2. The Number of Participants (group 1 only)

The sample size can be calculated for group 1 only, since the baseline cumulative incidence in group 2 will depend on surveillance outcomes, and often correspond to responses to a single case.

9.2.1. Sample size for stepped-wedge comparison of incidence decrease following MSAT

MSAT will be implemented in 60 villages with high 1-year cumulative incidence of *P. falciparum* clinical cases in 6 waves of 10 villages (1 wave per semester). Assuming a baseline cumulative incidence of 250 cases/1000/year, a population of 190 inhabitants per village with a 0.49 coefficient of variation in cluster size and an intra-cluster correlation coefficient of 0.12, the expected detectable difference between villages with and without intervention is <25 cases/1000/year for alpha=0.01 & beta=0.9.

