4. OBJECTIVES AND OUTCOME MEASURES

Objectives	Outcome Measures	Timepoint(s) of evaluation of this outcome measure (if applicable)
Primary Objective To measure the impact of URDT-based MSAT on P. falciparum incidence at village-level.	Adjusted incidence rate ratio before/after MSAT	Follow-up from MP opening to end of study
Secondary Objectives 1) To measure the impact of MSAT on prevalence of P. falciparum infection in malaria hotspots	1) Prevalence of P. falciparum infection measured in the village by URDT and by reference method (group 1)	1) Comparison between M0 survey (during MSAT) and M12 survey (12 months after)
2) To measure the impact of reactive MSAT on incidence of seasonal malaria peaks / outbreaks.	2) Change in the incidence dynamics over the transmission season (group 2)	2) Duration and height of seasonal peak before, during and after reactive intervention
3) Feasibility of MSAT as a programmatic tool and as a reactive strategy.	3) Coverage of village population with intervention	3) coverage based on census conducted before/during MSAT
4) % of infections treated compared to infections detected by reference method	4) % of P. falciparum positive samples by reference method which were positive by URDT and treated; % of P. falciparum negative samples by reference method which were positive by URDT and treated (group 1)	Group 1 only
Tertiary Objectives Retrospective comparison of MSAT versus MDA on prevalence and incidence of P. falciparum malaria	Cumulative incidence of falciparum malaria episodes before and after MDA/MSAT; prevalence of falciparum infection before and after MDA/MSAT	Entire incidence series

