6.4.3. Follow-up MSAT

A follow-up MSAT will be triggered if the estimated URDT prevalence of the M12 survey is $\geq 5\%$. It will follow the same procedures as the baseline MSAT.

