7.9. Definition of End of Study

The end of the study will be 12 months after the MSAT campaign if the estimated prevalence measured by URDT in the field is $< 5\%$, with the upper limit of the confidence interval below 10%. If the estimated prevalence is $\geq 5\%$, a new round of MSAT will be triggered. The follow-up will be conducted until 12 months after the last MSAT or 36 months after the first MSAT.

The threshold of 5% URDT prevalence corresponds to a 7.5% prevalence by uPCR, which was found to be indicating the presence of a substantial reservoir previously.

The MP will remain to continue diagnosis and treatment of fever cases as per the general METF procedures.

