9. STATISTICS AND ANALYSIS

9.1. Description of Statistical Methods

Coverage of intervention: the coverage of the intervention will be defined as the proportion of individuals screened by URDT divided by the total number of individuals present in the village during the next

Before/after MSAT yearly cumulative incidence and 95% Poisson confidence intervals will be calculated using:

- Numerator: the total number of *P. falciparum* cases reported during the weeks with an MP report.
- Denominator: the village population size measured during the MSAT * number of weeks with an MP report during the year (number of weeks of MP activity).

Analysis including the entire follow-up available for malaria posts will be conducted in order to provide adjusted estimates on the

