9.3. Analysis of Outcome Measures

Primary outcome: stepped-wedge comparison of incidence.

The incidence comparison will be conducted over a 2-year series of weekly incidence data, corresponding to 12 months before and 12 months after MSAT intervention. A generalized additive multilevel mixed model will be used to adjust for location, season, and temporal trend due to MP activity using uni-(seasonality, duration of MP activity in the village) or bivariate (latitude and longitude) splines, including random intercept and slopes at village level. MSAT intervention will be included in the model as a 0-1 variable. The incidence rate ratio obtain for this variable will quantify the average decrease in incidence after MSAT campaign compared to before.

Secondary outcome: before-after comparison of prevalence

For each village, the fractional change in prevalence before MSAT and 12 months after will be calculated and compared to 0% change. This change will be compared to the fractional change observed after MDA.

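### The 9.2.1 detectable difference (<25/1000/year at power 0.90) is tied to no analysis window; the time-adjusted 12+12-month analysis in 9.3 does not reach it, while section 4's full series roughly does

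*Combined protocol and SAP*

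**What the plan says.** Section 9.2.1 contains the only power statement for the primary outcome. For 60 villages treated in six waves of ten, one wave per semester, "the expected detectable difference between villages with and without intervention is <25 cases/1000/year for alpha=0.01 & beta=0.9". The inputs are a baseline of 250 cases/1000/year, 190 inhabitants per village, a coefficient of variation of village size of 0.49 and an intra-cluster correlation (ICC) of 0.12.

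Section 9.3 defines the primary comparison on a two-year weekly series, "corresponding to 12 months before and 12 months after MSAT intervention". The mixed model is to "adjust for location, season, and temporal trend due to MP activity", with village random intercepts and slopes, and "MSAT intervention will be included in the model as a 0-1 variable". The effect measure is an incidence rate ratio (IRR). The closing part of section 3 also speaks of comparison with the year before the intervention.

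Section 4 gives a different timepoint for the same outcome: "Follow-up from MP opening to end of study". Section 9.1 likewise announces adjusted estimates from all available MP follow-up. It also says that "yearly cumulative incidence and 95% Poisson confidence intervals will be calculated" for incidence before and after MSAT.

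On repeat rounds, 6.4.3 says "A follow-up MSAT will be triggered if the estimated URDT prevalence of the M12 survey" reaches 5%, and 7.9 says that in this case "a new round of MSAT will be triggered".

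**The concern.** A detectable difference belongs to a particular analysis. How much person-time each village contributes, and whether the effect must be separated from a time trend, can double the standard error. Section 9.2.1 fixes neither, and sections 4 and 9.3 point to different answers. A reader therefore cannot tell whether the primary analysis has 0.90 power for a 10% reduction (25 of 250) or much less.

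This matters for interpretation. If power for 25/1000/year were taken as 0.90 when it is nearer 0.3, a null or modest result would be read as excluding small effects that the analysis could not have seen.

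The window also changes what is estimated. Over the full series, a single 0-1 MSAT variable would combine time after the first round with time after a repeat round triggered at month 12.

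**Working it through.** **Inputs from 9.2.1:** 60 villages, 6 waves of 10, 190 people, size CV 0.49, ICC 0.12, rate 0.25 per person-year, alpha 0.01.

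**Assumptions:** two-sided alpha; beta=0.9 read as power 0.90; gamma-distributed village sizes; ICC constant over time.

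**Formulas**
- Between-village variance: 0.12 × 0.25 × 0.75 = 0.0225.
- Within-village variance per person-year: binomial 0.88 × 0.25 × 0.75 = 0.165; Poisson 0.25.
- Detectable difference = (2.5758 + 1.2816) × SE = 3.857 × SE.
- Power for 25/1000/year = Φ(25/SE − 2.576), with SE per 1000/year.
- SEs come from generalised least squares with a village intercept and the time terms named below.

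**Step 1: the plan's figure.** Take a stepped wedge of seven semesters with period effects, each village-semester credited with 190 person-years. The SE is 5.1 (binomial) or 6.3 (Poisson), so the detectable difference is 20 or 24. The stated <25 therefore reproduces.

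**Step 2: person-time.** A semester with 190 inhabitants supplies 190 × 0.5 = 95 person-years. The same seven-semester design then gives 28 / 34.

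**Step 3: the 9.3 window without a time term.** The village effect cancels in a before/after comparison with 190 person-years per side.
- Binomial: SE = √(2 × 0.165 / (190 × 60)) = 0.00538; × 3.857 = 20.8/1000/year.
- Poisson: SE = √(2 × 0.25 / (190 × 60)) = 0.00662; × 3.857 = 25.5/1000/year.

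**Step 4: the 9.3 window with time adjustment.** With half-year period effects the SE roughly doubles, to 11.4 / 13.6, giving 44 / 52 (one-sided alpha: 41 / 49). A monthly model closer to 9.3 has two seasonal harmonics, MP duration as a line or spline, and an assumed MP age at MSAT of 12-24 or 12-48 months. It gives 40-44 / 47-54. The Poisson figure reaches about 59 with a spline when MP ages are tightly clustered (assumed SD 3 months). With a time term present, village random slopes (assumed SD up to 100/1000/year per year) add about 1.

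**Step 5: the full series**, at 95 person-years per village-semester, with extra semesters before and after the wedge or MP ages spread over 12-48 months (assumed): 24-26 / 29-32.

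| Analysis | Detectable difference per 1000/year, binomial / Poisson | Power for 25/1000/year |
|---|---|---|
| 7 semesters, 190 person-years each | 20 / 24 | 0.99 / 0.92 |
| 7 semesters, 95 person-years each | 28 / 34 | 0.81 / 0.60 |
| 12+12 months, no time term | 21 / 25.5 | 0.98 / 0.88 |
| 12+12, period effects, 190 per semester | about 33 / 39 | 0.65 / 0.46 |
| 12+12, period effects, 95 per semester | 44 / 52 | 0.35 / 0.23 |
| 12+12, season and MP duration | 40-44 / 47-54 | 0.34-0.45 / 0.21-0.29 |
| Full series, extra semesters or MP ages 12-48 months | 24-26 / 29-32 | 0.88-0.94 / 0.69-0.77 |
| Full series, MP ages 12-24 months | 25-38 / 31-47 | 0.48-0.89 / 0.30-0.69 |

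**Step 6: the IRR scale** (Poisson, village and period effects).
- 9.3 window: SE(log IRR) is 0.063, so the detectable IRR is exp(−3.857 × 0.063) = 0.78, with power 0.18 for IRR 0.90.
- Full series: SE(log IRR) is about 0.032, so the detectable IRR is 0.88, with power about 0.76 for IRR 0.90.

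**Step 7: larger effects.** A 40% reduction from 250 is 100/1000/year. Even with a detectable difference of 59 (SE 15.3), power is Φ(100/15.3 − 2.576), above 0.99. At a baseline of 125 (the pre-MDA rate in 9.2.3) the 9.3 window gives 34 / 38, and power for a 40% reduction is again above 0.99. At the eligibility threshold of 84 it is about 0.95.

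**The case against.** The strongest reply is that 9.2.1 contains no wrong sum. The figure of <25 follows from its inputs if each semester counts as 190 person-years, and it nearly holds for the full series that section 4 and 9.1 describe. That stands. A reader might infer an arithmetic error, or that someone credited six months with a year of cases. The documents do not show this, because no formula is given; the person-time explanation only fits the figure.

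A reader might also take the 9.3 window as settled and conclude that the primary analysis has power of only 0.2 to 0.45 for the stated difference. The documents do not support that either, since two windows are on record.

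It is also fair that the larger figures need more than the window and the time adjustment. Keeping 190 person-years per semester gives 33 to 39; the rest comes from counting 95. That count follows from 190 inhabitants over half a year and from the 9.1 denominator (population times weeks reported), so it is not an arbitrary choice. Even the generous count misses 25.

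Poisson support is partial: 9.1 names Poisson intervals for the descriptive rates, and 9.3 names no error distribution for the model. Both variances are therefore shown, and the 12+12-month conclusion does not depend on which is used.

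**Conclusion.** The point holds as one of specification and consistency. The stated <25/1000/year at power 0.90 is attached to no window, and the protocol gives two.

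- **12+12 months (9.3), time-adjusted:** not reached. The range is about 33-39 on generous person-time and roughly 40-59 on actual person-time. Power for 25/1000/year is about 0.2 to 0.45, and at most about 0.65.
- **Full series (section 4, 9.1):** about right with binomial variance (24-26) and too favourable with Poisson variance (29-32). Both figures worsen if MP ages at MSAT are bunched.

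The upper ranges depend on the variance form, MP ages and spline choices, none of which the protocol gives. All figures assume a constant ICC. If correlation decays over time (cluster autocorrelation 0.95, assumed), they rise to about 32-50 for the seven-semester design and 51-78 in the 12+12-month window.

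It would be tempting to call the trial underpowered. The documents do not support that: the protocol discusses reductions of 40% and more, and power for those stays high in either window. This should be fixed because the stated sensitivity is relied on and is cheap to correct; the trial's viability is not in question.

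**What to change.** 1. Choose one primary data window and state it identically in section 4, 9.1 and 9.3. The 12+12-month window largely avoids repeat MSAT but is less precise. The full series is more precise but has to handle repeat rounds.
2. Recompute the 9.2.1 detectable difference for that window with the 9.3 time adjustment. Use 95 person-years per village-semester (190 per year) and the actual MP opening dates. State the formula, variance, sidedness, number of periods and ICC assumption, including whether correlation is constant over time. Preferably give the result also as an IRR, since that is the 9.3 effect measure. Write power=0.9 in place of beta=0.9. The ranges above show the size of the issue; they rest on assumed MP ages and should not be copied in as the new figure.
3. If the full series is chosen, give time after a repeat MSAT its own model term or censor it. The loss is small: about 25 / 31 with a separate term and 26-27 / 32-34 with censoring at month 12 (binomial / Poisson, MP ages 12-48 months assumed).

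Cost: one recalculation, aligned wording in four places and possibly one more model term. No extra villages are needed. The downside is a less favourable stated figure.

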9.2.2. Sample size for prevalence comparison

9.2.2.1. Sample size for prevalence decrease evaluation at village-level

For each village, the sample size required for M12 survey will be calculated to measure a 90% prevalence decrease from baseline prevalence by reference method, with a 95%CI width of 200% of expected M12 prevalence if its value is expected <2% and of 100% of expected M12 prevalence if its value is expected>2%. This should result in a sample size of 60 to 120 samples per village, depending on village size.

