7.7. Sample Handling

From the same finger-prick used to perform the URDT, 50µL of capillary blood will also be collected on an EDTA microtube, labelled with a participant sticker and transported to SMRU laboratories or stored immediately at -80°C in a dry-shipper liquid-nitrogen tank before transport. Upon reception at SMRU laboratories, the samples will be and stored at -80° C until processed for reference malaria detection by Quansys ELISA.

If the test is positive, a second finger prick will be conducted in order to collect an additional blood sample on filter paper (3x 1cm blood spots), labelled with a participant sticker, dried and stored in a plastic blister with silica gel. The DBS will be sent to MORU laboratory in Bangkok for DNA extraction and analysis by GENRE Mekong ([name], Mahidol Oxford Research Unit & Sanger Institute, UK) or MIVS-ACT ([name], Faculty of Tropical Medicine, Mahidol University, Thailand and Mahidol Oxford Research Unit) projects.

The follow-up survey 12 months after MSAT will follow the same procedures. The samples will be transported to SMRU laboratories and stored at -80°C until processed for reference malaria detection by Quansys ELISA.

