9.2.2.2. Number of villages required for prevalence comparison

We assume an average *P. falciparum* prevalence of 16% in group 1 villages using reference assay. Before/after comparison at village level will use samples from the same village but not necessarily the same individuals (correlation between paired observations set to 0). The sample size was calculated assuming 60 samples per cluster (the minimal number of samples collected at M12), an intra-cluster correlation coefficient of 0.15, the sample size required to identify a 50% decrease 12 months after intervention compared to baseline is 43 clusters for alpha=0.05 and 1-beta=0.8.

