19. APPENDIX D: UNPUBLISHED DATA ON URDT PERFORMANCE

This data was presented as a poster at the ASTMH Conference in November 2017.

Table 1: Comparison of the detection methods to uPCR

		uPCR result: Pf DNA+		Properties (%)	
		Neg	PF		
Lab uRDT result	Neg	1469	91	Specificity (Sp)= 98.9	98.3-99.4
	PF	16	115	Sensitivity (Se)= 55.8	48.8-62.7
Lab RDT result	Neg	1483	143	Sp= 99.9	99.5-100.0
	PF	2	63	Se= 30.6	24.4-37.7
Microscopy result	Neg	1483	148	Sp= 99.9	99.5-100.0
	PF	2	58	Se= 28.2	22.1-34.8
Field RDT result	Neg	1477	163	Sp= 99.9	99.5-100.0
	PF	2	43	Se= 20.9	15.5-27.1
Field uRDT result	Neg	1413	122	Sp= 99.3	98.7-99.7
	PF	10	80	Se= 39.6	32.8-46.7
Quansys ELISA	Neg	1427	35	Sp= 96.1	94.98-97.0
	PF	58*	171	Se= 83.0	77.2-87.9

[figure not shown]
* Plasmodium DNA found in 26/58 (45%) in the 1st step of uPCR, but PF was not characterized by the 2nd step.

Table 2: Reference test results in 16 uRDT positive, uPCR PF negative samples

Interpretation of combined HRP2- and parasite-reference tests

- Probable falciparum (or mixed) infections (Plasmodium DNA + PfHRP2).
- Insufficient evidence of falciparum infection (PfHRP2 without Plasmodium DNA or non-falciparum DNA without PfHRP2).
- No evidence of malaria infection (no DNA and no HRP2).

uPCR	Quansys HRP2		
	Neg	PF	Total
Negative	3	3	6
P. vivax	2	1	3
Plasmodium spp.	1	6	7
Total	6	10	16

Figure 1: Parasite densities detected by each method**Table 3: Detection of asymptomatic PF infections according to parasite density.**

Number of infections detected by method (for lab uRDT and RDT: corresponding % of uPCR infections detected).

Detected by:	Parasitemia category (parasites/mL)						Total
	<10 ²	10 ² -10 ³	10 ³ -10 ⁴	10 ⁴ -10 ⁵	10 ⁵ -10 ⁶	>10 ⁶	
uPCR	41	67	52	32	13	1	206
Lab uRDT	5 (12%)	30 (45%)	38 (73%)	28 (88%)	13 (100%)	1 (100%)	115 (56%)
Lab RDT	2 (5%)	6 (9%)	22 (42%)	19 (59%)	13 (100%)	1 (100%)	63 (31%)

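### The prevalence plan makes no allowance for ELISA false positives: at a 16% baseline, if the rate is the same at both surveys (2.2% to 3.9%), true 50% and 90% falls read as about 43% and 78%, or 38% and 68%

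*Combined protocol and SAP*

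**What the plan says.** The first secondary outcome (section 4) is the prevalence of *P. falciparum* infection by URDT and by a reference method, compared between M0 and M12 in group 1. Under section 7.7, samples from both surveys are "processed for reference malaria detection by Quansys ELISA".

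Both prevalence sample sizes rest on that method:
- Section 9.2.2.1 has the M12 survey in each village "calculated to measure a 90% prevalence decrease from baseline prevalence by reference method". The 95% CI width is 200% of the expected M12 prevalence if that is under 2%, and 100% if above. The section adds: "This should result in a sample size of 60 to 120 samples per village, depending on village size".
- Section 9.2.2.2 assumes a "prevalence of 16% in group 1 villages using reference assay", 60 samples per cluster, an intra-cluster correlation of 0.15 and "correlation between paired observations set to 0". It arrives at 43 clusters for a 50% fall.

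Section 9.3 then states: "For each village, the fractional change in prevalence before MSAT and 12 months after will be calculated and compared to 0% change". It does not name the test. It also plans a comparison with the change seen after MDA.

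Appendix D, Table 1 gives the ELISA a sensitivity of 83.0% (171/206) and a specificity of 96.1% against uPCR, with 58 positives among 1485 uPCR-negative samples. The footnote reads "Plasmodium DNA found in 26/58 (45%) in the 1st step of uPCR", but falciparum was not characterised in those samples.

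**The concern.** The outcome is named as infection, so a fall in ELISA prevalence will be read as a fall in infection. If a fixed share of uninfected people test positive at both surveys, that share does not shrink with infection, and the crude change understates the true one. The effect is largest where the plan hopes to do best: a 90% fall from 16% means an M12 value of 1.6%, which is less than either false-positive rate in Appendix D. That expected value also decides which width rule sets the M12 sample size.

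The comparison with MDA is exposed in another way. If its surveys used another assay, a difference between assays could pass for a difference between strategies.

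**Working it through.** **Inputs.** ELISA baseline a0 = 16%, 60 samples per cluster, ICC 0.15, correlation 0 (9.2.2.2). Se = 171/206 = 0.830 (Appendix D). False-positive rate f = 58/1485 = 3.9%. If all 26 samples with Plasmodium DNA count as infected, f = (58 - 26)/(1485 - 26) = 32/1459 = 2.2%.

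**The plan's own figures.** Going from 16% to 8% with two-sided alpha 0.05 and 80% power needs 258 samples per visit. The design effect is 1 + 59 × 0.15 = 9.85, and 258 × 9.85 / 60 = 42.4, so 43 clusters, as stated.

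For the village survey, n0 = 1.96² p(1 - p)/(width/2)² and n = n0/(1 + (n0 - 1)/N). The finite-population term is my assumption, taken from the remark on village size. With p = 1.6% and 200% width, n = 60, 106 and 121 for N = 80, 190 and 245, which matches the stated 60 to 120.

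**Model.** ELISA prevalence a = Se·p + f(1 - p), so p0 = (a0 - f)/(Se - f) = 17.1% (f = 2.2%) or 15.3% (f = 3.9%). With f and Se the same at both visits, Se cancels:

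apparent fall = true fall × (1 - f/a0)

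The factor is 1 - 0.0219/0.16 = 0.863, or 1 - 0.0391/0.16 = 0.756. Full clearance would read as 86% or 76%.

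| f at M0 | f at M12 | M12 ELISA, true 50% fall | reads as | M12 ELISA, true 90% fall | reads as | Power, 60 villages, true 50% fall |
|---|---|---|---|---|---|---|
| 2.2% | same | 9.10% | 43% | 3.57% | 78% | 81% |
| 3.9% | same | 9.95% | 38% | 5.12% | 68% | 69% |
| 2.2% | half | 8.09% | 49% | 2.50% | 84% | 91% |
| 3.9% | half | 8.15% | 49% | 3.19% | 80% | 91% |

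Power = Φ(|a0 - a12|/√(V/60) - 1.96), with V = [a0(1 - a0) + a12(1 - a12)] × 9.85/60. For example, with a12 = 9.10%, V = 0.2171 × 0.1642 = 0.0356, the standard error is 0.0244, and 0.0690/0.0244 - 1.96 = 0.87, giving 81%.

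At constant f, 80% power for halving infection needs 59-60 villages (f = 2.2%) or 79-80 (f = 3.9%).

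**Other baselines, constant f.** At 10%, true 50% and 90% falls read as 30-39% and 55-70%. At 25%, they read as 42-46% and 76-82%.

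**M12 sample size, village of 190, true 90% fall.** All four expected M12 values exceed 2%, so the 100% rule applies and n0 = 15.37(1 - p)/p. Constant f: p = 5.12% gives 114 and p = 3.57% gives 131. Halved f: p = 3.19% gives n0 = 466 and n = 135, and p = 2.50% gives n0 = 599 and n = 144. The plan's 1.6% gives 106.

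**URDT, constant f.** With false positives of 0.7% (field, 10/1423) or 1.1% (lab, 16/1485), true 50% and 90% falls read as 44-45% and 80-81%.

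**The case against.** The strongest reply is that the plan makes no error on its own scale. Sections 9.2.2.1 and 9.2.2.2 both speak of the reference method. A reader might infer that 43 clusters is a miscalculation. It is not: it is correct for halving ELISA prevalence. This stands.

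Second, 3.9% is the less favourable reading. Appendix D treats Plasmodium DNA together with PfHRP2 as probable falciparum or mixed infection. That legend sits under a table of 16 uRDT-positive samples, so applying it to the 26 is an inference, but a fair one. The same legend gives "Insufficient evidence of falciparum infection (PfHRP2 without Plasmodium DNA or non-falciparum DNA without PfHRP2"; it does not say no infection, so f could be below 2.2%. I therefore put 2.2% first and treat 3.9% as the upper case.

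Third, constant f is not established. The ELISA detects HRP2, which persists after treatment (6.3.2). The recent-treatment exclusion covers 7 days at MSAT (6.3.2) and 3 weeks at M12 (6.4.2). Both could lower f at M12, and if f halves, a 50% fall is read almost correctly. A reader might also infer that a 90% fall could never be observed. That follows only at constant f.

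Fourth, a reader might infer that the study is underpowered for prevalence. At f = 2.2% the 60 villages still give 81%. The shortfall needs f = 3.9%, constant, with little correlation between visits; an assumed correlation of 0.3 brings that case to 81%.

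What remains is that neither sample-size section nor 9.3 mentions the assay's error, although the protocol's own appendix reports it.

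**Conclusion.** The point holds as a conditional one about a secondary outcome. At a 16% ELISA baseline with f constant, the crude ELISA change is 0.86 (f = 2.2%) or 0.76 (f = 3.9%) of the true change, and the 1.6% implied by the 90% target lies below what the assay reads with no infection left. If f halves, the attenuation nearly disappears for a 50% fall and is moderate for a 90% fall. The documents do not settle which applies.

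At constant f the bias is towards no change, so the test against 0% is not made falsely positive. The percentages apply to an average village; section 9.3 computes one change per village, and these will vary with baseline. The URDT change is less affected. The primary incidence outcome and the URDT-based M12 decisions are not affected.

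A reader might infer that the MDA surveys used uPCR and that MSAT will look worse for that reason alone. Section 3 defines MDA hotspots by all-species prevalence, and section 7.9 gives a reservoir threshold in uPCR terms, but no section states the MDA assay. If it was uPCR, equal true 90% falls would differ by 12 to 22 points at constant f (90 - 78, 90 - 68), or 6 to 10 if f halves. The firm finding is only that the assay is not named.

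**What to change.** 1. In 9.2.2, state that the 50% and 90% falls are in ELISA prevalence. Give the power of 60 villages for a true 50% fall in infection under constant and halved f. Set the expected M12 ELISA prevalence with an explicit false-positive allowance over a range of f: about 2.5% to 5.1% after a true 90% fall, not 1.6%. Then apply the plan's own width rule or restate the precision.
2. In 9.3, name the test and report the crude ELISA and URDT changes first. Add one sensitivity analysis: a pooled M12/M0 ratio with prevalence (a - f)/(Se - f) at each visit, bounded at zero, carrying the uncertainty in Se and Sp. Show it for f = 2.2% and 3.9% constant, and for f halved at M12. Pool across villages because, after a true 90% fall at constant f, the M12 reading falls below f in about 36-40% of villages with 60 samples from binomial sampling alone.
3. Name the assay used in the MDA surveys. Compare fractional changes only on the same assay, or report the expected attenuation for each.

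Cost: mainly wording and analysis of data already planned.
- Following the width rule takes an average village from 106 to 114-131 M12 samples at constant f (135-144 if f halves). Keeping 106 means a stated width of about 109% to 132% at constant f.
- Adjusted intervals are wider. By simulation, for a true 50% fall with 60 villages, 60 samples per visit and correlation 0, the 95% interval goes from 16-63% to 20-73% (f = 2.2%), or from 9-59% to 13-77% (f = 3.9%).
- A constant-f correction over-corrects if f falls. With f halved, a true 50% fall becomes 57% (f = 2.2%) or 65% (f = 3.9%), and a true 90% fall becomes 98% or 106% before bounding. This is why the crude results stay first.
- The adjustment relies on Appendix D accuracy carrying over to these villages.
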